2.3.3. Overall Benefit/Risk Conclusion

The RSVPreF3 OA investigational vaccine is in clinical development. Considering the measures taken to minimize the risk to participants in this study, the potential risks are justified by the potential benefits linked to the development of this vaccine.

The benefits of FLU aQIV appear to outweigh its potential risks. The established favorable benefit-risk profile for FLU aQIV remains unchanged for the active immunization of individuals as of 65 YOA against influenza disease caused by influenza type A and type B viruses contained in the vaccine.

3. OBJECTIVES, ENDPOINTS AND ESTIMANDS

Table 5 Study objectives, endpoints and estimands (Amended: 13 December 2022)

Objectives	Endpoints and Estimands
Primary	
• To demonstrate the non-inferiority of the FLU vaccine when co-administered with the RSVPreF3 OA investigational vaccine compared to the FLU vaccine administered alone.	• HI antibody titers for each of the FLU vaccine strains expressed as group GMT ratio, one month after the FLU vaccine dose.
• To demonstrate the non-inferiority of the RSVPreF3 OA investigational vaccine when co-administered with the FLU vaccine compared to the RSVPreF3 OA investigational vaccine administered alone.	• RSV-A neutralization antibody titers expressed as group GMT ratio, one month after the RSVPreF3 OA investigational vaccine dose.
• To demonstrate the non-inferiority of the RSVPreF3 OA investigational vaccine when co-administered with the FLU vaccine compared to the RSVPreF3 OA investigational vaccine administered alone.	• RSV-B neutralization antibody titers expressed as group GMT ratio, one month after the RSVPreF3 OA investigational vaccine dose.
Secondary	
• To evaluate the non-inferiority of the FLU vaccine when co-administered with the RSVPreF3 OA investigational vaccine compared to the FLU vaccine administered alone.	• HI seroconversion status for each of the FLU vaccine strains expressed as SCR, one month after the FLU vaccine dose.
• To evaluate the humoral immune response to the RSVPreF3 OA investigational vaccine when co-administered with the FLU vaccine or administered alone.	• RSV-A neutralization antibody titers expressed as MGI at one month after the RSVPreF3 OA investigational vaccine dose. • RSV-B neutralizing antibody titers expressed as MGI at one month after the RSVPreF3 OA investigational vaccine dose.
• To evaluate the humoral immune response to the FLU vaccine when co-administered with the	• HI antibody titers for each of the FLU vaccine strains expressed as GMT, at Day 1 and Day 31.

Objectives	Endpoints and Estimands
RSVPreF3 OA investigational vaccine or administered alone.	
 HI seroconversion status for each of the FLU vaccine strains expressed as SCR, from Day 1 to Day 31. HI seroprotection status for each of the FLU vaccine strains expressed as SPR, at Day 1 and Day 31. HI antibody titers for each of the FLU vaccine strains expressed as MGI, one month after the FLU vaccine dose.

 To evaluate the safety and reactogenicity following administration of the RSVPreF3 OA investigational vaccine and the FLU vaccine, co-administered or administered alone. 	
 Percentage of participants reporting each solicited event with onset within 7 days after vaccine administration (i.e., the day of vaccination and 6 subsequent days). Percentage of participants reporting unsolicited AEs (pIMD, non-serious AE or serious AE) within 30 days after vaccine administration (i.e., the day of vaccination and 29 subsequent days). Percentage of participants reporting SAEs after vaccine administration (Day 1) up to study end (6 months after last vaccination). Percentage of participants reporting pIMDs after vaccine administration (Day 1) up to study end (6 months after last vaccination).

CCI

FLU vaccine refers to FLU aQIV

AE = adverse event; CCI = ; GMT = geometric mean titer; HI = hemagglutination inhibition; MGI = mean geometric increase; RSVPreF3 OA = respiratory syncytial virus PreFusion protein 3 older adult; SAE = serious adverse event; SCR = seroconversion rate; SPR = seroprotection rate; pIMD = potential immune-mediated disease; SCR = percentage of vaccinees who have either a HI pre-dose titer $< 1:10$ and a post-dose titer $\geq 1:40$ or a pre-dose titer $\geq 1:10$ and at least a 4-fold increase in post-dose titer.

SPR = percentage of vaccinees with a serum HI titer $\geq 1:40$ that usually is accepted as indicating protection.

[figure not shown]
MGI = geometric mean of the within-participant ratios of the post-dose titer over the pre-dose titer.

Details related to attributes of estimands covering intercurrent events, population and treatment definition are provided in Section 9.

4. STUDY DESIGN

4.1. Overall design

Figure 1 Study design overview

AE = adverse event; N = number of participants; pIMD = potential immune-mediated disease; RSV = respiratory syncytial virus; SAE = serious adverse event

- **Type of study:** self-contained.
- **Experimental design:** Phase III, randomized (ratio 1:1), open-label, multi-country study with 2 parallel groups (see [Figure 1](#)).
- **Study groups (refer to [Figure 1](#) and [Table 6](#) for an overview of the study groups):**
 - **Co-Ad (co-administration) group:** Participants receiving the RSVPreF3 OA investigational vaccine co-administered with FLU aQIV (referred to as FLU vaccine).
 - **Control group:** Participants receiving the FLU aQIV (referred to as FLU vaccine) and the RSVPreF3 OA investigational vaccine in a sequential manner.
- **Duration of the study:** ~6 months for participants in Co-Ad group; ~7 months for participants in Control group.
- **Primary completion date:** Day 61 (1 month after the RSVPreF3 OA investigational vaccine dose in Control group).
- **Control:** active comparator, i.e., sequential administration of licensed FLU vaccine and RSVPreF3 OA investigational vaccine.
- **Blinding:** open-label. Refer to Section [6.3.5](#) for details.
- **Data collection:** standardized electronic Case Report Form (eCRF). Solicited events will be collected using an electronic diary card (eDiary). Unsolicited AEs will be collected through questioning at study visits/contacts and reported into the eCRF. See Section [8.3.2](#) for details.
- **Safety monitoring:** the study will be conducted with oversight by the project Safety Review Team (SRT). Please refer to Section [10.1.5](#) for the SRT structure.
- **Vaccination schedule:**

Co-Ad group: Participants will be receiving both the RSVPreF3 OA investigational vaccine and FLU vaccine at Visit 1 (Day 1).

Control group: Participants will be receiving the FLU vaccine at Visit 1 (Day 1) and subsequently the RSVPreF3 OA investigational vaccine at Visit 2 (Day 31).

Table 6 **Study groups and interventions**

Study Groups	Number of Participants	Age (Min-Max)	Study Interventions
Co-Ad	~514	≥ 65 years	RSVPreF3 OA investigational vaccine
			FLU aQIV
Control	~514	≥ 65 years	RSVPreF3 OA investigational vaccine
			FLU aQIV

Co-Ad = co-administration; RSVPreF3 OA = respiratory syncytial virus PreFusion protein 3 older adult

4.1.1. Overview of the recruitment plan

No screening visit is planned for this study. The study is planned to be conducted at multiple sites in multiple countries. The recruitment plan will be defined by each participating site.

The recruitment plan may be adapted based on the actual number of participants enrolled in each country. In case a site would fall behind in participant recruitment, a redistribution of the enrollment target per site in the participating countries may be made. This would allow the other participating sites to enroll additional participants to ensure full and timely enrollment of the overall targeted number of participants specified in this protocol.

The procedures for participants' identification/recruitment must be approved by the Independent Ethics Committee (IEC)/Institutional Review Board (IRB) together with the material intended for participants' identification/recruitment and participants use. Refer to the Study Procedures Manual (SPM) for additional details.

4.1.2. Enrollment rules

Overall, participants will be enrolled in 3 age categories reflecting an approximate age distribution in the general population with a balance between males and females. It is therefore intended to enroll:

- Approximately 25% of participants 65-69 YOA, ~40% of participants 70-79 YOA and ~10% of participants ≥ 80 YOA. The remaining 25% can be distributed freely across the 3 age categories.
- Approximately 40% of participants from each sex; the remaining 20% can be distributed freely between the 2 sexes.

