6.3.3. Intervention allocation to the participant

An automated Internet-based system, SBIR will be used for randomization and for identification of intervention material. The randomization algorithm will use a minimization procedure accounting for age (65-69, 70-79 or ≥ 80 years) and center. Minimization factors will have equal weight in the minimization algorithm. Refer to Section 4.1.2 for the enrollment rules.

Once a participant identification number is allocated, the randomization system will determine study group and will provide the study intervention number to be used for the

first dose. The study intervention numbers to be used for subsequent dosing will be provided by the same automated Internet-based system (SBIR).

When SBIR is not available, please refer to the SBIR user guide or SPM for specific instructions.

Refer to the SPM for additional information about the study intervention number allocation.

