9. STATISTICAL CONSIDERATIONS

9.1. Statistical hypotheses (Amended 13 December 2022)

Statistical hypotheses are associated with the confirmatory primary NI objectives, which will be tested sequentially to control overall Type I error.

Global type I error is controlled at 2.5% (1-sided).

The non-inferiority margins associated to each objective are provided in [Table 18](#).

Table 18 Study objectives and null hypothesis (Amended: 13 December 2022)

Objectives	Null hypothesis
Primary	
• To demonstrate the non-inferiority of the FLU vaccine when co-administered with the RSVPreF3 OA investigational vaccine compared to the FLU vaccine administered alone.	• True Group GMT ratio between the FLU vaccine (Control group) divided by the RSVPreF3 OA investigational vaccine when co-administered with the FLU vaccine (Co-Ad group) in HI antibody titers for each of the FLU vaccine strains one month after the FLU vaccine dose is above 1.5.
• To demonstrate the non-inferiority of the RSVPreF3 OA investigational vaccine when co-administered with the FLU vaccine compared to the RSVPreF3 OA investigational vaccine administered alone.	• True Group GMT ratio between the RSVPreF3 OA investigational vaccine (Control group) divided by the RSVPreF3 OA investigational vaccine when co-administered with the FLU vaccine (Co-Ad group) in RSV-A neutralization antibody titers one month after the RSVPreF3 OA investigational vaccine dose is above 1.5.
• To demonstrate the non-inferiority of the RSVPreF3 OA investigational vaccine when co-administered with the FLU vaccine compared to the RSVPreF3 OA investigational vaccine administered alone.	• True Group GMT ratio between the RSVPreF3 OA investigational vaccine (Control group) divided by the RSVPreF3 OA investigational vaccine when co-administered with the FLU vaccine (Co-Ad group) in RSV-B neutralization antibody titers one month after the RSVPreF3 OA investigational vaccine dose is above 1.5.

Co-Ad = co-administration; FLU vaccine refers to FLU aQIV; GMT = geometric mean titer; HI = hemagglutination inhibition; RSVPreF3 OA = respiratory syncytial virus PreFusion protein 3 older adult

Statistical testing of each endpoint will be organized sequentially to control overall Type I error.

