4. STATISTICAL ANALYSES

4.1. General Considerations

4.1.1. General Methodology

95% CI for proportion will be based on exact Clopper-Pearson CI [[Clopper](#), 1934].

95% CI for group difference in proportion will be based on Miettinen and Nurminen CI [[Miettinen](#), 1985].

The group adjusted GMT ratio will be based on a back transformation of group contrast in an ANCOVA model applied to the logarithm-transformed titers.

Primary Analysis: The ANCOVA model will include the treatment group and age category (age at vaccination: 65-69, 70-79 or ≥ 80 years) as fixed effects and the pre-dose log-10 titer as regressors.

Sensitivity Analysis: The ANCOVA model will include the treatment group and age category (age at vaccination: 65-69, 70-79 or ≥ 80 years) as fixed effects, center as the random effect and the pre-dose log-10 titer as regressors.

95% CI for GMT and GMT ratio will be based on a back transformation of student CI for the mean and difference of means (for GMT ratio) respectively of log-transformation (i.e., $10^{\wedge}CI$).

4.1.2. Definition:

- For all endpoints:

The baseline value will be the latest pre-dose assessment with a non-missing value, including those from unscheduled visits. If time is not collected, Day 1 assessments are assumed to be taken prior to first dose and used as baseline.

MG1 (mean geometric increase): The geometric mean of the within participant ratios of the post-dose titer over the pre-dose titer.

- For the RSV antigens:

A seronegative participant will be defined as a participant whose antibody titer/concentration is below the cut-off value of the assay. A seropositive participant is a participant whose antibody titer/concentration is greater than or equal to the cut-off value of the assay.

- For the FLU antigens:

SCR (seroconversion rate): The percentage of vaccinees who have either a HI pre-dose titer $< 1:10$ and a post-dose titer $\geq 1:40$ or a pre-dose titer $\geq 1:10$ and at least a four-fold increase in post-dose titer.

HI SPR (seroprotection rate): The percentage of vaccinees with a serum HI titer $\geq 1:40$ that usually is accepted as indicating protection.

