4.2.2. Main analytical approach

The 2-sided 95% CI for group adjusted GMT ratio will be derived from **an ANCOVA model on \log_{10} transformed titer**. The model will include the treatment group and age category (age at vaccination: 65-69, 70-79 or ≥ 80 years) as fixed effects, and the pre-dose \log_{10} -transformed titer as covariate. Missing data will not be replaced. Titers below the assay cut-off will be replaced by half the assay cut-off, titers above the upper limit of quantification (ULOQ) will be replaced by the ULOQ.

Success criteria for non-inferiority and testing sequence:

The following testing sequence will be used:

1st sequence:

- The upper limit of the 2-sided 95% CI of the GMT ratio (Control group divided by Co-Ad group) for each of the FLU vaccine strains are ≤ 1.5 .

AND

- The upper limit of the 2-sided 95% CI of the GMT ratio (Control group divided by Co-Ad group) for RSV-A neutralization antibodies is ≤ 1.5 .

2nd sequence:

- The upper limit of the 2-sided 95% CI of the GMT ratio (Control group divided by Co-Ad group) for RSV-B neutralization antibodies is ≤ 1.5 .

Testing will progress in the 2nd sequence only if the 1st sequence is a success, so that no further adjustment of alpha is required.

Here is an example of SAS code that will be used:

```
proc mixed data=data_in;
  class agecat trt_grp;
  model log10(titer day x) = log10(pre_dose) agecat trt_grp;
  lsmeans trt_grp/cl pdiff alpha=0.05;
  run;
```

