6.1.2. Demographic and Baseline Characteristics

The median, mean, range and standard deviation of age (in years) at first vaccination will be computed by group. The center distribution, distribution of participants in each age category (65-69 YOA, 70-79 YOA, ≥ 70 YOA and ≥ 80 YOA) geographical ancestry and sex composition will be presented. This analysis will be based on the ES, the PPS and on the **CCI**

The number and percentages of participants with medical history classified by the MedDRA Primary SOC, HLT and PTs will be tabulated by group for the ES.

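### Sex is an enrollment target and is recorded for everyone, but no ANCOVA uses it: a nearly free, small precision gain for the six primary GMT ratios

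*Protocol*

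**What the plan says.** Protocol 4.1.2 sets recruitment aims for two characteristics, age and sex. For sex: "Approximately 40% of participants from each sex; the remaining 20% can be distributed freely between the 2 sexes". The aim applies to the study as a whole, not to each group.

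Age is then carried through the design. Protocol 6.3.3 describes a "minimization procedure accounting for age (65-69, 70-79 or ≥ 80 years) and center". SAP 4.2.2 states: "The model will include the treatment group and age category (age at vaccination: 65-69, 70-79 or ≥ 80 years) as fixed effects", with pre-dose log10 titer as covariate, and the sample code reads "model log10(titer day x) = log10(pre_dose) agecat trt_grp". Protocol 9.3.1 gives the same model. The sensitivity model (SAP 4.1.1 and 4.2.3) keeps these terms and adds only center, as a random effect. Subgroup tables (SAP 4.3.1.2 and 4.3.2) are by age.

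Sex is collected in the eCRF (Protocol 8.2.1.1). In the SAP it appears only in the baseline description, where "geographical ancestry and sex composition will be presented" (SAP 6.1.2). No primary, sensitivity or subgroup analysis uses it. One model form serves all six primary ratios: four HI strains, RSV-A and RSV-B.

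**The concern.** Two characteristics are managed at enrollment, but only one is used in the analysis, and the documents do not say why. The enrollment rule limits the overall sex mix to roughly 40–60% of either sex. It does not balance sex between groups, and neither does the minimization.

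Any sex difference in response that remains after age and pre-dose titer therefore stays in the residual variance of every primary ratio. What is at stake is precision only. The HI comparisons are where it could count, because Table 21 of the protocol gives each strain a type II error of 2.5% against 0.1% for each RSV endpoint. The four strains thus carry nearly all of the stated 10% global type II error.

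**Working it through.** **Inputs from the documents** (Protocol 9.5, SAP 5): 462 evaluable per group; SD of log10 titer 0.6 (each FLU strain) and 0.45 (RSV-A, RSV-B); true ratio 1.05 (log10 = 0.0212); margin 1.5 (log10 = 0.1761); one-sided alpha 2.5%.

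**Assumed, not in the documents:** a sex difference *b* in post-dose log10 titer, given age and pre-dose titer, of 0 to 0.2; a 50:50 sex split; the planning SD used as the residual SD; independence between strains.

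**1. The plan's own figures.** For HI, SE = 0.6 × √(2/462) = 0.0395. The noncentrality is (0.1761 − 0.0212)/0.0395 = 3.92. The noncentral t gives 97.50% per strain (stated 97.5%). With SD 0.45 the result is 99.95% (stated 99.9%). Global power is 1 − 4 × 0.0250 − 2 × 0.0005 = 89.9%, or 90.3% as a product (stated about 90%). The figures reproduce. For four strains alone, 0.9750⁴ = 90.4%.

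**2. Size of chance imbalance.** The SD of the group difference in the proportion of one sex is √(2 × 0.5 × 0.5/462) = 3.3 percentage points. The 95% range is ±1.96 × 3.3 = about ±6.4 points. A simulated minimization on age and center alone (40 centers assumed, 924 participants) gave nearly the same: SD 3.4 points, 95% range ±6.3.

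**3. Validity with sex omitted.** With the true ratio at the margin, 400,000 simulated trials per scenario (sex GMT ratio 1.5 or 2.0, SD 0.45 or 0.6) gave a one-sided type I error of 2.46–2.49%. The nominal level holds.

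**4. Gain from including sex.** Sex accounts for a variance of b² × 0.25. The adjusted SD is √(SD² − 0.25 b²), and the CI narrows by 1 − adjusted SD/SD. For HI (SD 0.6):

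| b (log10) | Sex GMT ratio (10^b) | Adjusted SD | CI narrower by | Power per strain | Four strains |
|---|---|---|---|---|---|
| 0 | 1.00 | 0.6000 | 0% | 97.50% | 90.4% |
| 0.05 | 1.12 | 0.5995 | 0.1% | 97.52% | 90.4% |
| 0.10 | 1.26 | 0.5979 | 0.3% | 97.58% | 90.7% |
| 0.20 | 1.58 | 0.5916 | 1.4% | 97.81% | 91.5% |

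For RSV (SD 0.45), b = 0.20 gives an adjusted SD of √(0.2025 − 0.01) = 0.4387. That CI is 2.5% narrower, but power is already 99.95% and gains almost nothing.

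**5. Cost in degrees of freedom.** The primary model uses five parameters (intercept, group, two for age, one for pre-dose titer), leaving 924 − 5 = 919. Sex takes one more.

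**The case against.** The best counter-argument is that nothing here is wrong. The enrollment rule concerns a representative sample; it neither stratifies nor says that sex predicts titer. The models adjust for the allocation factors (age in the primary model, center in the sensitivity model) and for pre-dose titer, so leaving out sex breaks no rule in the documents. Pre-dose titer already absorbs any sex difference present before vaccination. The documents give no sex effect on response, so the benefit could be zero. Both documents were amended in December 2022, and changing a confirmatory model in an open-label study needs a reason. All of this stands. It limits the point to an optional improvement but does not remove it.

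Three stronger readings are tempting and are not supported.

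- A reader might infer that the ratios are biased or the type I error inflated. Step 3 shows otherwise for the randomized comparison. The confirmatory analysis uses the per-protocol set, and the RSV exclusion rules do differ by group, because only Control participants need a second vaccination visit and a Day 61 sample. But nothing in the documents links exclusion to sex.
- A reader might take the shift from an unlucky imbalance as a further harm. A 6.4-point imbalance with b of 0.05 to 0.2 moves a ratio by 10^0.0032 to 10^0.0128, or 0.7 to 3%. That is the same sampling error that the narrower interval removes, so it must not be counted twice. Nor is the planning ratio of 1.05 a yardstick for it: that is an assumed true ratio, not an allowance for imbalance. The largest shift, 0.0128 log10, is about one sixth of the HI CI half-width of 1.96 × 0.0395 = 0.077.
- A reader might infer that the study is underpowered. The stated power reproduces without any credit for covariates.

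**Conclusion.** The plan is valid as written on this point. Sex is a complete baseline variable that the analysis leaves unused, and using it would bring a small precision gain: HI intervals 0 to 1.4% narrower, and four-strain power from 90.4% to at most 91.5%.

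Both ranges rest on an assumed sex difference of 0 to 0.2 log10 given baseline, for which the documents offer no evidence either way; at the lower end there is no gain. Independence between strains is also assumed, although all four are measured in the same participants. If age and pre-dose titer bring the residual SD below 0.6, the proportional gain would be larger, but power would start higher. This is a worthwhile refinement of low priority.

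**What to change.** Add sex, as recorded in the eCRF, as a fixed effect beside age category and pre-dose log10 titer in Protocol 9.3.1 and in SAP 4.1.1 and 4.2.2, for all six titers. In the sample code, add it to the class and model statements. Make the same addition to the center model in SAP 4.2.3.

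If the sponsor prefers not to change the confirmatory model, for instance because enrollment is under way (the documents do not say), pre-specify one further sensitivity ANCOVA in SAP 4.2.3 that adds sex to the primary model.

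In either case the choice should be fixed before post-dose titers are available to the analysis team, since adding sex after seeing an imbalance would be data-driven. The cost is one degree of freedom and a one-term edit to protocol and SAP. No new data are needed, and the sample size stays the same.

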4.1.3. Caregiver support

Study participants may decide to assign a caregiver to help them fulfill the study procedures. Please refer to the [Glossary of terms](#) for the definition of a caregiver.

A caregiver can be appointed by the participant at any time during the study, when the participant feels it is necessary. Each caregiver should receive the caregiver information letter before providing support to the study participant. Ideally, a single caregiver should be appointed by the participant but, in some situations, it may happen that several caregivers will support a study participant throughout the conduct of the study. This should be recorded in the source documents. However, every effort should be done to ensure that only one caregiver enters the data into the eDiary to allow for timely completion.

Caregivers may help the study participants to perform some practical study procedures such as receiving or making phone calls to site staff, planning study visits, transcribing responses to diaries, transportation to and from the study site etc. However, at no time, should the caregiver evaluate the participant's health status while completing diaries or

make decisions on behalf of the participant. At the first study visit (Visit 1) the site staff should inform the participant of the possibility to appoint a caregiver. Then at subsequent study visit(s), the site staff should check again with the participant if he/she wishes to appoint a caregiver or if there were or will be changes in caregiver.

Please refer to the SPM for additional information on the appointment of a caregiver.

